**Study protocol**

**Effectiveness of acupuncture for cyclical mastalgia (CM)**

**CFH2022-3-7132**

**2022.5.28**

# Study protocol

## Effectiveness of acupuncture for cyclical mastalgia (CM)

### 1. Participant Flow

#### Recruitment Details

Patients are planned to be recruited via outpatient clinic, advertisements on websites and posters from hospitals and a chat group using WeChat (WeChat, Version: 8.0.21, Tencent, Shenzhen, China). The recruitment date is from July 1, 2022 to December 31, 2023. The Recruitment location will be performed at three hospitals in Beijing: (1)Beijing Traditional Chinese Medicine Hospital Pinggu Hospital, (2)Pinggu huangsongyu Community hospital, and (3)Pinggu Xiagezhuang Community hospital. All potentially eligible women with CM will be invited to the trial and be able to contact the researchers with the provided phone number. Eligible participants will be introduced to the research contents in detail and informed about the potential benefits and possible risks of this study, then personal information including age, marriage, menstrual, and medical history are cautiously recorded. After 2 weeks of reflection, patients are invited to meet with the research physician to discuss any remaining questions and sign the informed consent.

#### Pre-assignment Details

Eligible participants will be introduced to the research contents in detail and informed about the potential benefits and possible risks of this study, then personal information including age, marriage, menstrual, and medical history are cautiously recorded. After 2 weeks of reflection, patients are invited to meet with the research physician to discuss any remaining questions and sign the informed consent.

#### Arm/Group Information

##### Arm/Group Title

108 patients will be randomly divided into MA (manual acupuncture)and SA(sham acupuncture) (1:1 allocation ratio)

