##### Arm/Group Description

##### MA group

Acupuncture rationale was based on the theory of TCM, which is closely related to the liver. When reviewing the literature on breast pain, people believe that "Stagnation of liver qi and stagnation of Qi and blood" is a good explanation for the important mechanism of breast pain attack. We will select Ashi points (the most obvious local pain over the breast), Tanzhong(CV17), bilateral Wuyi (ST15), Rugen (ST18), Tianzong(SI11), Geshu (BL17), Ganshu(BL18), Hegu(LI4), Sanyinjiao (SP6) and Taichong (LR3)in this trial. The location of the above acupoints will be based on the nomenclature and location of acupuncture points drafted by the National Standard of the People' s Republic of China (GB/T 12 346-2006) [1]. Sterile single-use stainless steel needles (size 0.3 mm × 40 mm) (Hwato brand, Suzhou Medical Appliance Factory, China) will be utilized. After local skin disinfection with 75% alcohol wipes while patients are in a sitting position, then fix the adhesive pad (to ensure the implementation of a blind method, the acupuncture group is placed with the same

fixed adhesive pad as the sham acupuncture group). Acupuncturists will insert needles horizontally into the Wuyi(ST15), Rugen (ST18), and Ashi points toward the mammary duct to a depth of 15 – 20 mm; horizontally into tanzhong(CV17) downward to a depth of 5 – 10 mm, perpendicularly into Hegu(LI4), Sanyinjiao (SP6), Tianzong(SI11), and Taichong (LR3) to a depth of approximately 15 – 25 mm. Obliquely into Geshu (BL17) and Ganshu(BL18) to a depth of approximately 15-20mm. The depth of needling will vary based on the participant's body size. After insertion, all needles will be manually manipulated (equal manipulations of twirling, lifting, and thrusting) to achieve De qi sensation, which is defined as a composite of unique needling sensations, including soreness, numbness, distention, or heaviness felt by both participants and acupuncturists [2]. All the needles will be retained for 30 min and then gently removed.

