### **SA group**

Sham acupuncture rationale was based on taking nonmeridian and nonpoints of ganglion segments different from breast pain area. The SA group will use a special needle in which the tip is blunt and the pedestal is opaque. There is an adhesive pad below the base to ensure that the whole pedestal can adhere to the points. Participants will receive superficial touch at bilateral sham GV8(Jinsuo), sham GV7(Zhongshu), sham GV6(Jizhong), sham GV5(Xuanshu), sham GV4(Mingmen), sham BL37(Yinmen), and sham BL57(Chengshan). Sham GV8, GV7, GV6, GV5, GV4 (≈ 20mm to horizontally outside of GV8, GV7, GV6, GV5, GV4), BL37, and BL57 (≈ 10mm to horizontally outside of BL37 and BL57). After local skin disinfection with 75% alcohol wipes while patients are in a prone position, then fix the adhesive pad, and give the patient a verbal prompt to inform the patient of the need for acupuncture manipulation. Sham acupuncture needles of 0.30 × 40 mm size (Hwato brand, Suzhou Medical Appliance Factory, China) will be inserted the adhesive pad at a depth of 2 – 3 mm until the needles can standstill, the needles will touch the skin and not be inserted into the skin, then lift and twist each point evenly for 3 times, make the subject feel the similar sensation of deqi. All the needles will be retained for 30 min and then gently removed.

All patients will undergo treatment two weeks before menstruation, and treatment will be stopped at the onset of menstruation. Three times a week, six times a menstrual cycle, and 3 consecutive menstrual cycles for a total of 18 sessions after baseline. All acupuncturists have a license and at least 5 years of acupuncture practice. Patients will be treated separately with a curtain drawn and their companions waiting outside the clinic. Patients in both groups will receive advice on breast pain education and lifestyle modification. During the process of the trial, patients are not allowed to take other specialized medication or therapies for CM, details should be recorded in the case report form (CRF).

1. Standardization Administration of the People's Republic of China. GB/T12346-2006, Nomenclature and Location of Acupuncture Points [S]. 2006.

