### **3. Outcome Measures**

#### **Primary outcome**

The primary outcome in this trial is the change in the average of VAS-BP scores in the first 2 weeks of menstruation, recorded in the patient daily diary.

The VAS-BP will be measured using a 10cm linear VAS with 0 representing no pain and 10 the worst imaginable pain from baseline at weeks 4, 8, and 12.

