### **Statistical analysis**

Sample size estimation was based on changes in the breast pain VAS(VAS-BP) score. According to the pre-trial, the VAS-BP score significantly decreased by  $2.98 \pm 0.95$  in MA group compared to  $2.35 \pm 0.97$  in the SM group after treatment from baseline. In the current trial, we assume a significance level  $\alpha = 0.05$  and power  $(1-\beta) = 0.90$ , and providing for a two-sided outcome, at least 42 participants will be required for each group, as calculated by PASS version 11.0 (NCSS, LLC, Kaysville, UT, USA), assuming a two-tailed test with a 20% drop-out rate, a total of 108 patients (54 in each group) will be recruited.

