## Statistical Analysis Plan

Statistical methods for primary and secondary outcomes

We will use SPSS 22.0 software (IBM SPSS Statistics; IBM Corp, Somers, NY) to perform all statistical analyses following the intention-to-treat principle. The CI will be established at 95%, and the significance level at 0.05. For continuous data, the data will be presented as mean  $\pm$  standard deviation when normally distributed or presented as median (IQR) when not normally distributed. Statistical comparisons will be performed by the independent-sample t tests or Wilcoxon rank-sum test for continuous data and by X-test or Fisher exact test for categorical data, as appropriate. A p-value  $<0.05$  will be considered statistically significant.

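### Three hospitals recruit, but no stratification by site is described and the primary test has no site term: a cost in precision, not a bias

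*Combined protocol and SAP*

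**What the plan says.** - **Sites.** Recruitment Details states "The Recruitment location will be performed at three hospitals in Beijing" and names one traditional Chinese medicine hospital and two community hospitals. Enrolment per hospital is not given, nor is the place of treatment.
- **Allocation.** The Arm/Group Title section says "108 patients will be randomly divided into MA (manual acupuncture)and SA(sham acupuncture) (1:1 allocation ratio". The available text gives no sequence generation, blocks, strata or concealment.
- **Analysis.** The protocol's statistical methods and the SAP both say "Statistical comparisons will be performed by the independent-sample t tests or Wilcoxon rank-sum test for continuous data". Neither has a site or acupuncturist term, and the protocol marks additional analyses as not applicable.
- **Operators.** The SA group section says "All acupuncturists have a license and at least 5 years of acupuncture practice". It does not say how many there are or whether each treats both arms. In the MA group, "all needles will be manually manipulated (equal manipulations of twirling, lifting, and thrusting) to achieve De qi sensation".
- **Outcome.** The primary outcome is the "change in the average of VAS-BP scores in the first 2 weeks of menstruation, recorded in the patient daily diary", so it is self-rated.

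**The concern.** Women recruited at a traditional Chinese medicine hospital may differ from those at community hospitals in their response to needling or sham. If so, the site differences enter the residual variance of an unadjusted test, and an unstratified list lets a hospital's arms become uneven by chance. Both are avoidable. The planning difference is only 0.63 VAS points, so extra residual variance matters. There is also an unanswered question about operators: the treatment is hands-on and the outcome subjective, and the text does not show whether operators are crossed with arms.

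**Working it through.** **The plan's own figure.** The sample-size section gives mean falls of 2.98 (SD 0.95) and 2.35 (SD 0.97). The difference is 0.63 and the pooled SD is √((0.95² + 0.97²)/2) = 0.960. It then says "at least 42 participants will be required for each group" and "assuming a two-tailed test with a 20% drop-out rate, a total of 108 patients (54 in each group) will be recruited". With these inputs, two-sided α 0.05 and 90% power, I get 49 per arm (normal) or 50 (t), not 42; 42 per arm gives 84–85% power. The drop-out step gives 42/0.8 = 52.5, so 53 per arm and 106 in total, close to 108. The shortfall is a separate matter. Below I use 54 per arm with no losses, where the two-sided t test has power 0.92.

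**Cost of leaving site out.** Assume 0.960 is the within-site SD, the first hospital holds a fraction f of the women, and its mean change differs from the other two by s. The total SD is √(0.960² + f(1−f)s²). Example with sizes 36/36/36 and s = 1.0: f(1−f)s² = 0.222, SD = √(0.922 + 0.222) = 1.070, SE = 1.070 × √(2/54) = 0.206, and 0.63/0.206 = 3.06, giving power 0.86.

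| Assumed site sizes | s = 0.5, no site term | s = 1.0, no site term | With site term |
|---|---|---|---|
| 36/36/36 | 0.91 | 0.86 | about 0.92 |
| 64/22/22 | 0.91 | 0.85 | about 0.92 |
| 86/11/11 | 0.91 | 0.88 | about 0.92 |

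Simulations of 20,000 trials per case, with 54:54 allocated regardless of site, agree to within about 0.01. In them the unadjusted test's type I error stays close to 0.05, and in the runs where it was recorded the mean estimate under no effect is about 0. With no site difference, adding the term changes power by about 0.005 or less.

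**Chance of uneven arms.** Site sizes are again assumed. With the total fixed at 54:54, the number of MA women at a hospital of size n is hypergeometric (108 women, 54 in MA, n drawn).

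| n | Arms differ by 6 or more | Arms differ by 8 or more |
|---|---|---|
| 24 | 24.7% | 10.4% |
| 30 | 28.3% | 13.2% |

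Independent coin flips would give 31% and 15% for n = 24, and 36% and 20% for n = 30. Those figures ignore the planned 54:54 total.

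**What one imbalance does.** A 15:9 split at a hospital that differs by s moves the unadjusted estimate by s × (15 − 9)/54. That is 0.11 points at s = 1.0 and 0.06 at s = 0.5, against the planned 0.63.

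**Operators, only if each arm had its own.** Assume three acupuncturists per arm, so m = 54/3 = 18 women each. The design effect is 1 + 17 × ICC, and the type I error is 2(1 − Φ(1.96/√DE)). At ICC 0.01, 0.05 and 0.10 the design effect is 1.17, 1.85 and 2.70, and the type I error is 0.07, 0.15 and 0.23. The documents give neither the number of acupuncturists nor an ICC, and do not say that the arms are split this way.

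**The case against.** The strongest reply is that the documents are silent, and silence is not a design. The allocation line sits under an arm title and gives only random division and the ratio. Some pages and the flow chart are not in the available text, so stratification may exist. That stands: the supportable statement is that none is described.

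Four stronger readings are tempting and fail:

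- A reader might infer that site is confounded with arm. Women are randomised individually, so site lines up with arm only by chance, which the planned test's error rate already covers.
- A reader might infer that acupuncturists specialise by arm. Nothing says so, and nothing excludes it.
- A reader might infer that the community hospitals are the smaller sites, or that each site's own staff give the lifestyle advice. The text gives no enrolment figures and does not name who gives the advice.
- A reader might infer that operators are unregulated beyond licence and experience. The arm descriptions also fix points, needle size, manipulation and a 30-minute retention, with depth ranges and a shared adhesive pad.

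It can also be said that the loss is modest, and that it vanishes if the hospitals do not differ. That is correct and limits the point's weight. It does not remove it, because the stated analysis has no site term and adding one costs almost nothing.

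**Conclusion.** The point holds as a minor, inexpensive improvement to the stated design and analysis. At an assumed site difference of 0.5 VAS points the loss of power is about one percentage point; at 1.0 point it is roughly four to seven. These figures assume 54 evaluable women per arm, one hospital differing from the other two, and a planning SD that excludes site variation. If the pre-trial SD already contains site variation, the unadjusted power is 0.92 and a site term would raise it, so the direction of the advice is unchanged. Validity of the test is not in question on the site issue. The operator issue is a request for clarification: it would become serious only if different acupuncturists served each arm, because their effect could not then be separated from the treatment's.

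**What to change.** 1. In the Arm/Group Title section, state that randomisation is 1:1 in concealed permuted blocks of varying size, stratified by the three hospitals. If this is already done, stating it closes that part.
2. In the protocol's statistical methods and in the SAP, include site as a factor in the primary VAS-BP comparison, for example by a linear model with arm and site. If the rank test is used, use a version stratified by site.
3. Where the acupuncturists' qualifications are given, confirm that every acupuncturist treats women in both arms, and record an operator code in the CRF at each session.

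Items 1 and 2 cost a three-stratum list and two degrees of freedom. Item 3 costs one CRF field and, if it is not already the practice, training each acupuncturist in both procedures.

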##### Arm/Group Description

##### MA group

Acupuncture rationale was based on the theory of TCM, which is closely related to the liver. When reviewing the literature on breast pain, people believe that "Stagnation of liver qi and stagnation of Qi and blood" is a good explanation for the important mechanism of breast pain attack. We will select Ashi points (the most obvious local pain over the breast), Tanzhong(CV17), bilateral Wuyi (ST15), Rugen (ST18), Tianzong(SI11), Geshu (BL17), Ganshu(BL18), Hegu(LI4), Sanyinjiao (SP6) and Taichong (LR3)in this trial. The location of the above acupoints will be based on the nomenclature and location of acupuncture points drafted by the National Standard of the People' s Republic of China (GB/T 12 346-2006) [1]. Sterile single-use stainless steel needles (size 0.3 mm × 40 mm) (Hwato brand, Suzhou Medical Appliance Factory, China) will be utilized. After local skin disinfection with 75% alcohol wipes while patients are in a sitting position, then fix the adhesive pad (to ensure the implementation of a blind method, the acupuncture group is placed with the same

fixed adhesive pad as the sham acupuncture group). Acupuncturists will insert needles horizontally into the Wuyi(ST15), Rugen (ST18), and Ashi points toward the mammary duct to a depth of 15 – 20 mm; horizontally into tanzhong(CV17) downward to a depth of 5 – 10 mm, perpendicularly into Hegu(LI4), Sanyinjiao (SP6), Tianzong(SI11), and Taichong (LR3) to a depth of approximately 15 – 25 mm. Obliquely into Geshu (BL17) and Ganshu(BL18) to a depth of approximately 15-20mm. The depth of needling will vary based on the participant's body size. After insertion, all needles will be manually manipulated (equal manipulations of twirling, lifting, and thrusting) to achieve De qi sensation, which is defined as a composite of unique needling sensations, including soreness, numbness, distention, or heaviness felt by both participants and acupuncturists [2]. All the needles will be retained for 30 min and then gently removed.

### **SA group**

Sham acupuncture rationale was based on taking nonmeridian and nonpoints of ganglion segments different from breast pain area. The SA group will use a special needle in which the tip is blunt and the pedestal is opaque. There is an adhesive pad below the base to ensure that the whole pedestal can adhere to the points. Participants will receive superficial touch at bilateral sham GV8(Jinsuo), sham GV7(Zhongshu), sham GV6(Jizhong), sham GV5(Xuanshu), sham GV4(Mingmen), sham BL37(Yinmen), and sham BL57(Chengshan). Sham GV8, GV7, GV6, GV5, GV4 (≈ 20mm to horizontally outside of GV8, GV7, GV6, GV5, GV4), BL37, and BL57 (≈ 10mm to horizontally outside of BL37 and BL57). After local skin disinfection with 75% alcohol wipes while patients are in a prone position, then fix the adhesive pad, and give the patient a verbal prompt to inform the patient of the need for acupuncture manipulation. Sham acupuncture needles of 0.30 × 40 mm size (Hwato brand, Suzhou Medical Appliance Factory, China) will be inserted the adhesive pad at a depth of 2 – 3 mm until the needles can standstill, the needles will touch the skin and not be inserted into the skin, then lift and twist each point evenly for 3 times, make the subject feel the similar sensation of deqi. All the needles will be retained for 30 min and then gently removed.

All patients will undergo treatment two weeks before menstruation, and treatment will be stopped at the onset of menstruation. Three times a week, six times a menstrual cycle, and 3 consecutive menstrual cycles for a total of 18 sessions after baseline. All acupuncturists have a license and at least 5 years of acupuncture practice. Patients will be treated separately with a curtain drawn and their companions waiting outside the clinic. Patients in both groups will receive advice on breast pain education and lifestyle modification. During the process of the trial, patients are not allowed to take other specialized medication or therapies for CM, details should be recorded in the case report form (CRF).

1. Standardization Administration of the People's Republic of China. GB/T12346-2006, Nomenclature and Location of Acupuncture Points [S]. 2006.

## **Type of Units Assigned**

### **Period(s)**

The duration of the trial is 38 weeks for each patient, including a 2-week baseline assessment (week 0-2), 12-week treatment period (week 1-12), and 24-week follow-up (week 13-36).

### **2. Baseline Characteristics**

Personal information including age, marriage, menstrual, and medical history and a series of questionnaire including VAS-BP in the first two weeks of menstruation, the number of nominal days of breast pain (NDBP) two weeks before menstruation, World Health Organization Quality Of Life Scale-Short Form (WHOQOL-BREF) scores, breast glandular section thickness and breast duct width three days before menstruation are cautiously recorded.

### **3. Outcome Measures**

#### **Primary outcome**

The primary outcome in this trial is the change in the average of VAS-BP scores in the first 2 weeks of menstruation, recorded in the patient daily diary.

The VAS-BP will be measured using a 10cm linear VAS with 0 representing no pain and 10 the worst imaginable pain from baseline at weeks 4, 8, and 12.

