#### **Secondary outcomes**

1. The changes in the number of nominal days of breast pain (NDBP) during 2 weeks before menstruation from baseline at weeks 4, 8, 12.

2. The changes of WHOQOL-BREF scores from baseline at weeks 12. The

WHOQOL-BREF china version will be used to evaluate the QOL of the participants. The WHOQOL-BREF Questionnaire consists of 26 items, in which the first and second questions of the questionnaire are about the QOL and health status in general. The next 24 questions assess the QOL in four dimensions: physical health (7 items); psychological (6 items); environment (8 items); and social relationships (3 items). Each item is answered on a five-point scale. A higher score denotes a better quality of life [3-4].

3. The changes in breast glandular section thickness, and breast duct width three days before menstruation from baseline at weeks 12.

Mammary ultrasonography will be used to observe breast glandular section thickness, and breast duct width. All ultrasound image acquisition work is completed by the same ultrasound physician with at least 5 years of professional practice.

4. Patients' global improvement assessment: It will be assessed by a 7-point self-reporting scale ranging from 1 to 7: significantly reduced, moderately reduced, slightly reduced, no change, slightly aggravated, moderately aggravated, and significantly aggravated. The proportion of patients reporting "significantly reduced" or "moderately reduced" is recorded as the response rate of overall efficacy.

5. Patients' acceptability toward acupuncture at the end of the 1st treatment at week 1 and the last treatment at week 12. The acceptability of acupuncture will be assessed among participants in the MA group using a 3-point index: unacceptable (0 points), acceptable (1 point), and easy to accept (2 points). Those who regard acupuncture as unacceptable will report the reasons. The average score will be calculated after the 2

assessments.

6. Blindness assessment: within 3 min after the last treatment session at week 12, all participants will be asked to answer the question do you think you have received acupuncture treatment and choose the answer between the options of Yes or No.

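### The primary VAS-BP window is worded as the fortnight after menses onset, while treatment, NDBP and ultrasound sit before it; one 2-week baseline cannot hold both windows

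*Combined protocol and SAP*

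**What the plan says.** Protocol section 3 (Primary outcome) defines the endpoint as "the change in the average of VAS-BP scores in the first 2 weeks of menstruation, recorded in the patient daily diary", assessed "from baseline at weeks 4, 8, and 12". Section 2 (Baseline Characteristics) repeats the window and sets a different one beside it: "VAS-BP in the first two weeks of menstruation, the number of nominal days of breast pain (NDBP) two weeks before menstruation".

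The other time-anchored elements are premenstrual:
- Treatment, both groups (schedule under SA group): "All patients will undergo treatment two weeks before menstruation, and treatment will be stopped at the onset of menstruation". There are six sessions per cycle for three cycles, 18 in all.
- NDBP (Secondary outcomes, item 1): "number of nominal days of breast pain (NDBP) during 2 weeks before menstruation from baseline at weeks 4, 8, 12".
- Ultrasound (Secondary outcomes, item 3): "breast duct width three days before menstruation from baseline at weeks 12".

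The Period(s) section gives one 2-week baseline, 12 weeks of treatment and 24 weeks of follow-up, 38 weeks in total. It labels the baseline weeks 0-2 and treatment weeks 1-12. Table 1 instead runs from week -2 to week 36, with consent at -2, allocation at 0, VAS-BP and NDBP in every column, and ultrasound at 0 and 12. The SAP names tests but no VAS-BP window.

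**The concern.** Taken at its words, the primary endpoint averages pain over the fortnight that begins at menses onset, a different part of the cycle from the one that is treated and in which the related outcomes are measured. If that is intended, the baseline as scheduled is too short for the outcomes it must serve. If it is not intended, the primary endpoint is misworded. At a 28-day cycle the two readings use entirely different diary days: one scores the fortnights in which sessions are given, the other the treatment-free fortnights that follow. These are different endpoints, and the diary average cannot be programmed with confidence until the plan says which one is meant.

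**Working it through.** **Inputs.** 2 + 12 + 24 weeks (Period(s)); 3 cycles of 6 sessions (SA group); 14-day VAS-BP and NDBP windows (sections 2 and 3); consent at week -2 and allocation at week 0 (Table 1). No cycle length is stated in the available text, so it is inferred and then varied.

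**The plan's own figures.** 2 + 12 + 24 = 38 weeks, which matches Table 1: 36 - (-2) = 38. Sessions: 3 x 6 = 18. Implied cycle: 12 x 7 / 3 = 28 days.

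**Overlap.** For cycle length C, the literal VAS-BP window is cycle days 1 to 14 and the premenstrual window is days C-13 to C. Shared days = max(0, 28 - C). Distinct days needed for both = min(28, C), which exceeds 14 whenever C exceeds 14.

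**Sessions inside the scored windows.** Assume three sessions a week, at days 0, 2, 4, 7, 9 and 11 of each premenstrual fortnight. Read literally, the three on-treatment windows open after 6, 12 and 18 sessions. The third contains none, so the count is twice the number of sessions per block that fall in cycle days 1-14. At 21 days the block starts on cycle day 8, with sessions on days 8, 10, 12, 15, 17 and 19; three fall inside, giving 2 x 3 = 6.

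| Cycle (days) | Shared days | Days needed for both | Sessions in literal windows | Sessions in premenstrual windows |
|---|---|---|---|---|
| 21 | 7 | 21 | 6 of 18 | 18 of 18 |
| 24 | 4 | 24 | 4 of 18 | 18 of 18 |
| 26 | 2 | 26 | 2 of 18 | 18 of 18 |
| 28 | 0 | 28 | 0 of 18 | 18 of 18 |
| 35 | 0 | 28 | 0 of 18 | 18 of 18 |

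**Fitting the literal window to Table 1 at 28 days.** The documents do not say which cycle day week 0 is, so both natural choices were tried.
- *Week 0 = menses onset* (onsets at weeks 0, 4, 8, 12). Premenstrual windows are weeks -2 to 0, 2-4, 6-8 and 10-12. Literal VAS-BP windows are weeks 0-2, 4-6, 8-10 and 12-14. The scheduled baseline holds NDBP and ultrasound but no VAS-BP days; all 14 VAS-BP baseline days follow allocation.
- *Week 0 = start of treatment* (onsets at weeks -2, 2, 6, 10). Literal VAS-BP windows are weeks -2 to 0, 2-4, 6-8 and 10-12, so the VAS-BP baseline precedes allocation. The premenstrual baseline is weeks -4 to -2, before consent. The first ultrasound day after consent is day 14 - 3 = 11, inside the first treatment block (days 0-14). Baseline NDBP would have to be recalled.

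**The premenstrual reading, for comparison.** With week 0 at menses onset, weeks -2 to 0 serve VAS-BP, NDBP and ultrasound together, and the on-treatment windows close at weeks 4, 8 and 12 after 6, 12 and 18 sessions.

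**Do the week labels decide it?** Three premenstrual blocks span 2C + 14 days; at 28 days this is 70 days, or 10 weeks. Acceptability is assessed "at the end of the 1st treatment at week 1 and the last treatment at week 12" and blinding "within 3 min after the last treatment session at week 12". At 28 days a first session in week 1 puts the last in week 10, and a last session in week 12 puts the first in week 3. So the week-12 label fits onset at week 0, and the week-1 label fits treatment starting at week 0. Counting the first session as day 0, the last is day 2C + 11 and week 12 starts at day 77. Both labels therefore fit once 2C + 11 is at least 77, that is, C of about 33 days or more.

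**The case against.** The best defence is that this is a drafting slip for the fortnight before menstruation. The premenstrual reading fits one 14-day baseline and the visit weeks, whereas with week 0 at menses onset the third literal window runs to week 14, past the last on-treatment assessment. That is a good argument and may well be right. It does not settle the matter, because the phrase occurs in two sections and in section 2 stands in the same sentence as a differently worded NDBP window.

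Several stronger inferences are tempting and should not be drawn:
- *That the endpoint has no definition.* The VAS-BP window is given twice, consistently. What the documents show is an unexplained mismatch with the other windows and no week-to-cycle map.
- *That the window could be chosen after the data are seen.* This would require diaries kept across both fortnights, which the available text does not say.
- *That a recalled NDBP baseline breaks the plan.* Only VAS-BP is said to come from a daily diary; section 2 lists NDBP among questionnaires and Table 1 marks it at the consent visit. Recall is not excluded. The missing ultrasound day stands, but only if week 0 is the start of treatment.
- *That the first and last session weeks are incompatible.* This is so at 28 days, not at about 33 days or more.

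One part of the document and Figure 1 were not available, so nothing is said about cycle-length eligibility, and statements of absence are limited to the text that could be read.

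**Conclusion.** The point holds as an internal inconsistency in the primary endpoint. That one 2-week baseline cannot contain both windows in full is true for any cycle longer than 14 days and does not rest on the 28-day inference. The 0 of 14 shared days does rest on it, or on a longer cycle; at assumed shorter cycles the overlap is 2 to 7 days. The contrast of 0 against 18 of 18 sessions in the scored windows is likewise for 28 days, with 2 to 6 under the literal reading at cycles of 26 down to 21 days.

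Followed literally, the schedule either takes the VAS-BP baseline wholly after allocation or leaves no pre-treatment ultrasound day after consent. The documents do not establish which window the authors meant.

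A reader might also infer a loss of power. The documents do not support that: they give no VAS-BP by cycle phase, and the sample-size section does not say which window produced the pre-trial changes of 2.98 and 2.35.

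**What to change.** In protocol sections 2 and 3 and in the SAP, define VAS-BP as the mean of daily diary scores over stated days relative to menses onset, and reconcile that window with those for NDBP, ultrasound and treatment.

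- *Simplest option:* days -14 to -1, the same as NDBP, in the baseline cycle and in cycles 1-3. One 14-day baseline then serves all three measures. Cost: wording of the outcome, diary instructions and week labels; no extra visits, weeks or patients.
- *If the post-onset window is intended:* say so, and provide a baseline covering both windows (28 days at the nominal cycle), completed before allocation. If week 0 is menses onset, weeks -2 to 2 fit within the 38 weeks, but allocation moves to week 2. If week 0 is the start of treatment, the baseline grows by 2 weeks and the total from 38 to 40.

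In either case, state how weeks 4, 8 and 12 map to cycles 1-3 and whether a visit week opens or closes its window. Reconcile the week labels: baseline weeks 0-2 overlapping treatment weeks 1-12 in Period(s), against -2 to 0 in Table 1, and the stated weeks of the first and last sessions.

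Confirm which window the pre-trial changes of 2.98 and 2.35 came from. If it was not the one finally chosen, the assumption behind 42 per group must be re-checked.
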